5.3.1 Safety Considerations

- Treatment with ruxolitinib can cause thrombocytopenia, anemia and neutropenia. Manage thrombocytopenia by reducing the dose or temporarily interrupting ruxolitinib. Platelet transfusions may be necessary. Subjects developing anemia may require blood transfusions and/or dose modifications of ruxolitinib. Severe neutropenia (ANC less than $0.5 \times 10^9/L$) was generally reversible by withholding ruxolitinib until recovery. Perform a pre-treatment complete blood count (CBC) and monitor CBCs every 2 to 4 weeks until counts are stabilized, and then as clinically indicated.
- Serious bacterial, mycobacterial, fungal and viral infections have occurred. Delay starting therapy with ruxolitinib until active serious infections have resolved. Observe subject receiving ruxolitinib for signs and symptoms of infection and manage promptly.
- Tuberculosis infection has been reported in patients receiving ruxolitinib. Observe subjects receiving ruxolitinib for signs and symptoms of active tuberculosis and manage promptly. Prior to initiating ruxolitinib, subjects should be evaluated for tuberculosis risk factors, and those at higher risk should be tested for latent infection. For subjects with evidence of active or latent tuberculosis, consult a physician with expertise in the treatment of tuberculosis before starting ruxolitinib. The decision to continue ruxolitinib during treatment of active tuberculosis should be based on the overall risk-benefit determination.
- Progressive multifocal leukoencephalopathy (PML) has occurred with ruxolitinib treatment. If PML is suspected, stop ruxolitinib and evaluate.
- Advise subjects about early signs and symptoms of herpes zoster and to seek treatment as early as possible if suspected.
- Hepatitis B viral load (HBV-DNA titer) increases, with or without associated elevations in alanine aminotransferase and aspartate aminotransferase, have been reported in patients with chronic HBV infections taking ruxolitinib. The effect of ruxolitinib on viral replication in patients with chronic HBV infection is unknown. Subjects with chronic HBV infection should be treated and monitored according to clinical guidelines.
- Non-melanoma skin cancers including basal cell, squamous cell, and Merkel cell carcinoma have occurred in patients treated with ruxolitinib. Perform periodic skin examinations.

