6 DOSE MODIFICATIONS

6.1 Phase I and Phase II Dose Modification and Dose Delay

Dose reductions are not permitted during Cycle 1 of Phase I unless the subject experiences a DLT. The subject may continue protocol therapy if the toxicity resolves, and the subject can be managed by a dose modification as detailed in this section. However, the occurrence of the DLT will be counted toward the assessment of the MTD. Dose reductions are permitted in subsequent cycles of Phase I and during all cycles of Phase II for clinically significant hematologic and non-hematologic toxicities. Held doses are not made up.

The prophylactic use of G-CSF and platelet transfusions in Cycle 1 of the dose escalation cohorts in Phase I is not permitted. Dose adjustments are permitted according to rules described in this section. Dose modifications different from those stated in the protocol should only be made in consultation with the Sponsor-Investigator; unless required for immediate subject safety.

Administration of the study drugs will be discontinued in the event of a treatment-related toxicity that persists despite appropriate dose reductions or any other toxicity that, in the opinion of the Investigator, warrants discontinuation.

Toxicity will be assessed using the CTCAE version 4.03 (Appendix [18.2](#)).

All dose modifications should be based on the worst preceding toxicity

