6.3 Dose Modification Guidelines for Carfilzomib and Ruxolitinib during a Cycle of Therapy

Hematologic Toxicity	Recommended Action
-----------------------------	---------------------------

 • Grade 3^a or 4 Neutropenia (ANC < 1000 mm³) • Grade 4 Thrombocytopenia (Platelets < 25,000 mm³) or any grade with bleeding. 	
 • Withhold ruxolitinib and carfilzomib and re-evaluate in one week • If recovered to Grade 1 or better before next scheduled dose, continue ruxolitinib and carfilzomib at same dose level. • If recovered to Grade 2 neutropenia or Grade 3 thrombocytopenia, reduce ruxolitinib and carfilzomib dose by one dose level. Reductions in one drug and not the other may be considered with alternating dose reductions for subsequent occurrence. • If tolerated, the reduced dose may be escalated to the previous dose at the discretion of the physician.
Non-Hematologic Toxicity	Recommended Action
Cardiac Toxicity Grade 3 or 4, new onset or worsening of: 
 • congestive heart failure; • decreased left ventricular function; • or myocardial ischemia 	
 • Withhold carfilzomib until resolved or returned to baseline. • After resolution, consider restarting carfilzomib at a reduced next dose level if appropriate. • If tolerated, the reduced dose may be escalated to the previous dose at the discretion of the physician.
Pulmonary Hypertension	
 • Withhold carfilzomib until resolved or returned to baseline. • Restart at the dose used prior to the event or next dose level at the discretion of the physician. • If tolerated, the reduced dose may be escalated to the previous dose at the discretion of the physician.
Pulmonary Complications 
 • Grade 3 or 4 	
 • For drug related Grade 3 or 4 pulmonary toxicity, permanently discontinue carfilzomib.

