6.5 Criteria for Initiation of a New Cycle of Therapy

For a new cycle of treatment to begin, the subject must meet the following criteria:

- ANC must be $\geq 1,000/\text{mm}^3$.
- Platelet count must be greater than or equal to $25,000/\text{mm}^3$
- All other non-hematologic treatment-related toxicity (except for alopecia) must have resolved to \leq Grade 1 or to the subject's baseline condition, with the exception of fatigue which must have resolved to \leq Grade 2.

If the subject fails to meet the above-cited criteria for initiation of the next cycle of treatment, dosing should be delayed for 1 week. At the end of that time, the subject should be re-evaluated to determine whether the criteria have been met. If the subject continues to fail to meet the above-cited criteria, delay therapy and continue to re-evaluate. The maximum delay before treatment should be discontinued will be 3 weeks or at the discretion of the Investigator. Phase II/Run-In only: beginning with Cycle 1, disease evaluation results should be available prior to dosing on Day 1 of each cycle until initiation of ruxolitinib (Phase II/Ruxolitinib).

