9 ADVERSE EVENTS

9.1 Adverse Event

An adverse event (AE) is any symptom, sign, illness or experience that develops or worsens in severity during the course of the study. Intercurrent illnesses or injuries should be regarded as AEs. Abnormal results of diagnostic procedures are considered to be AEs if the abnormality:

- results in study withdrawal
- is associated with a serious AE
- is associated with clinical signs or symptoms
- leads to additional treatment or to further diagnostic tests
- is considered by the Investigator to be of clinical significance

9.2 Serious Adverse Event (SAE):

An event is "serious" if it involves considerable detriment or harm to one or more persons (who may or may not be participants) or required intervention to prevent one or more persons from experiencing considerable detriment or harm. SAEs include:

- Death
- Life-threatening experience – Disease or condition where the likelihood of death is high unless the course of the disease/condition is interrupted or diseases/conditions with potentially fatal outcomes where the end point of the clinical trial analysis is survival
- Inpatient hospitalization or prolongation of hospitalization
- Persistent or significant disability/incapacity

- Congenital anomaly/birth defect in subject's offspring
- Any other important medical event that, based upon appropriate medical judgment, may jeopardize the participant, and may require medical or surgical intervention to prevent one of the outcomes listed above. Examples include allergic bronchospasm requiring intensive treatment in an emergency room or at home, blood dyscrasias or convulsions that do not result in inpatient hospitalization, the development of drug dependency or drug abuse, suicidal ideation or attempts, or the unintentional revealing of some genetic information to insurers.

9.2.1 Related:

An event is "related" if, in the opinion of the Investigator, it was definitely or possibly was caused by the research activity.

9.2.2 Unexpected:

An event is "unexpected" when its specificity, nature, severity or incidence is not accurately reflected in the investigator's brochure or Package Insert previously reviewed and approved by the IRB. Examples include a lower rate of response to treatment or a side effect that is more severe than initially expected.

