9.5 Abnormal Laboratory Values Defined as AEs

An abnormal laboratory value is considered to be an AE if the laboratory abnormality is characterized by any of the following:

- Results in discontinuation from the study
- Requires treatment, modification of study drug dose, or any other therapeutic intervention

- Is judged by the Investigator to be of significant clinical impact/importance
- Meets the criteria for a DLT as defined in Section 4.2.1.3

If a laboratory abnormality is one component of a diagnosis or syndrome, then only the diagnosis or syndrome should be recorded as an AE. If the laboratory abnormality was not a part of a diagnosis or syndrome, then the abnormality should be recorded as the AE.

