13.4.3 Safety Analyses

Treatment administration will be summarized descriptively in terms of cumulative dose administration and dose intensity of ruxolitinib (adjusting for dose delays and reductions). Additionally, the relative dose intensity will be calculated in terms of the actual dose intensity as percent of the intended dose intensity. The maximum grade for each type of adverse event will be recorded for each subject and treatment-emergent adverse events (TEAEs) will be identified. TEAEs are defined as follows:

- An adverse event that occurs after treatment start that was not present at the time of treatment start; or
- An adverse event that increases in severity after treatment start if the event was present at the time of treatment start.

TEAEs will be summarized using frequencies and proportions, and these will be reviewed to determine patterns. Additionally, the relationship of the adverse event(s) to the study treatment will be taken into consideration.

Clinical laboratory tests (hematology, chemistry, coagulation panel, BNP), vital signs, and ECHO/MUGA/cardiac MRI (ejection fraction (%)) will be summarized with descriptive statistics.

Phase II Stopping Rule

It is estimated that the composite rate of Grade 3/4/5 AESIs (as defined in Section 13.2.10) in relapsed or refractory multiple myeloma patients treated with carfilzomib plus dexamethasone is approximately 0.30³⁰. If it becomes evident that the Grade 3/4/5 AESI rate convincingly exceeds 0.30, the study will be halted. Enrollment will be suspended if the posterior probability of the Grade 3/4/5 AESI rate exceeding 0.30 is 0.75 or higher. The prior distribution for this monitoring rule is beta (3,7). This means that our prior assumption regarding the proportion of Grade 3/4/5 AESI's is 0.30, and there is 90% probability that this proportion is between 0.098 and 0.550. The operating characteristics of the stopping rule are given in the following table and are based on 5000 simulations.

Operating Characteristics of the Stopping Rule

Number of Subjects with an AESI	Number of Treated Subjects	Posterior Probability: Pr(AESI Rate>0.30 Data)
3	5	0.781
4	8	0.779
5	11	0.761
6	14	0.777

7	17	0.767
8	20	0.768
9	23	0.772
10	26	0.770
11	29	0.761

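### A Grade 3 platelet count without bleeding need not be recorded as an adverse event, and no laboratory-derived grade table is planned, so the reported Grade 3 thrombocytopenia rate can be too low

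*Combined protocol and SAP*

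**What the plan says.** **Analysis.** Section 13.4.3 builds its toxicity table from adverse events: "The maximum grade for each type of adverse event will be recorded for each subject", and TEAEs are then given as frequencies and proportions. Laboratory tests, including hematology, appear in one sentence with vital signs and cardiac imaging, which ends "ejection fraction (%)) will be summarized with descriptive statistics". Section 13.2.10 lists selected quantitative laboratory values as a safety endpoint. Neither section names a grade table or a shift table.

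**Recording.** Section 9.5 makes an abnormal laboratory value an adverse event if it leads to discontinuation, needs treatment, a dose change or another intervention, meets a DLT criterion, or "Is judged by the Investigator to be of significant clinical impact/importance". Section 9.1 is similar for diagnostic results. It adds association with an SAE or with symptoms, and further diagnostic tests, and ends with a result that "is considered by the Investigator to be of clinical significance".

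**Managing low platelets.** Section 5.3.1 advises: "Manage thrombocytopenia by reducing the dose or temporarily interrupting ruxolitinib". It gives no grade threshold. The table in Section 6.3 requires a hold only for Grade 4 thrombocytopenia (<25,000/mm³) or for any grade with bleeding. After a hold it treats Grade 3 as a level at which dosing may resume: "If recovered to Grade 2 neutropenia or Grade 3 thrombocytopenia, reduce ruxolitinib and carfilzomib dose by one dose level". For a new cycle, Section 6.5 says "Platelet count must be greater than or equal to" 25,000/mm³. In Phase I, Section 6.1 adds: "Dose reductions are not permitted during Cycle 1 of Phase I unless the subject experiences a DLT".

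**The concern.** The Grade 3 thrombocytopenia rate will come from a table of recorded adverse events, yet no rule in the protocol makes an uncomplicated Grade 3 count an adverse event. If such counts are not recorded, the published rate is too low. If sites differ in what they record, the rate partly reflects recording practice.

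Thrombocytopenia is among the first harms that Section 5.3.1 names for ruxolitinib, and Section 1.2 makes safety and tolerability of the combination a secondary objective. A reader judging whether the triplet can be given at the chosen dose would rely on this figure. Only descriptive safety reporting is at stake.

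**Working it through.** The plan states no figure to reproduce. The check is to follow one count through every rule that could make it an adverse event or show it in an output.

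**Step 1: the band.** Section 4.2.1.3 places Grade 3-4 thrombocytopenia below 50,000/mm³, and Section 6.3 places Grade 4 below 25,000/mm³. Grade 3 is therefore 25,000 to <50,000/mm³.

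**Step 2: the rules, for a count in that band without bleeding.**

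| Rule | Condition | Met? |
|---|---|---|
| DLT (4.2.1.3) | Grade 3-4 with clinically significant bleeding | No |
| Hold of both drugs (6.3) | Grade 4, or bleeding | No |
| Carfilzomib hold (5.1.3) | ≤25,000/mm³ | Only at exactly 25,000 |
| Delay of new cycle (6.5) | <25,000/mm³ | No |
| AESI (13.2.10) | Five terms, none for platelets | No |
| Ruxolitinib advice (5.3.1) | Thrombocytopenia, no grade stated | At the investigator's choice |
| Adverse event (9.1, 9.5) | Action, further tests, symptoms, SAE, discontinuation, DLT or judgment | Not by rule |

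Apart from the single value 25,000, nothing in the band forces an action. Recording therefore rests on discretionary action or on judgment. In Phase I Cycle 1 the action route is narrower, because Section 6.1 bars dose reduction without a DLT and bars prophylactic platelet transfusion. That leaves interruption of ruxolitinib, further tests and judgment.

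**Step 3: what is outside the gap.** Grade 3-4 neutropenia, and thrombocytopenia that is Grade 4 or accompanied by bleeding, trigger the Section 6.3 holds and so are largely captured.

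**Step 4: the outputs.** The TEAE table shows only recorded events. A mean or median platelet count by visit would satisfy the laboratory sentence in Section 13.4.3 and would not show how many subjects reached Grade 3.

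**Step 5: size per missed subject.** Section 13.3 pools both phases for ruxolitinib safety. If both phases fill, n = 18 + 30 = 48.

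- Pooled: 1/48 = 2.1 percentage points.
- Phase II alone: 1/30 = 3.3 percentage points.

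These denominators are targets for evaluable subjects. The safety population is everyone who starts ruxolitinib, so it may be larger if subjects are replaced, or smaller if a phase does not fill.

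**Step 6: illustration.** Reported rate = true rate × share recorded. The documents give neither factor, so both are assumed:

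| True uncomplicated Grade 3 rate | 100% recorded | 75% | 50% | 25% |
|---|---|---|---|---|
| 20% | 20% | 15% | 10% | 5% |
| 40% | 40% | 30% | 20% | 10% |

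With complete recording the understatement is zero.

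**The case against.** The best reply is that this is a matter for table shells.

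- **Laboratory data are already planned output.** Hematology will be summarized whatever is recorded as an adverse event, and descriptive statistics could include minima or grade counts. That is true, but nothing commits to them.
- **Investigators have reasons to record.** Section 9.6 describes Grade 3 in general as severe or medically significant, which fits the importance criterion in Section 9.5. Section 5.3.1 advises reduction or interruption, and Section 6.1 allows reductions for clinically significant hematologic toxicity in later Phase I cycles and throughout Phase II. A count acted on in these ways is an adverse event. This stands in part: some cases, perhaps many, will be captured, but none by rule.
- **Training may close the gap.** Section 11 promises protocol-specific eCRF guidelines, which could fix how laboratory grades are recorded. They are not in the documents, so they cannot be credited or ruled out.
- **The recovery line in Section 6.3 loses no cases.** A subject held for Grade 4 is already recorded at a higher grade. That is right. The line shows only that the protocol tolerates Grade 3 counts when dosing resumes.
- **No decision turns on this.** The trial has no comparator arm, and its decision rules do not use the rate. This is also right, and it is why the point is minor.

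Section 9.8, which has sites report adverse events of all grades, does not help, because it applies only once a value counts as an adverse event.

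**Conclusion.** The concern holds as a minor weakness in safety reporting. The recording rule can produce a low, investigator-dependent Grade 3 thrombocytopenia rate, and no committed output would reveal it.

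The conclusion is that the rate can be understated. Whether it will be, and by how much, cannot be known from the documents. Each unrecorded subject costs 2.1 points of 48 or 3.3 points of 30, assuming the phases fill to those numbers. The point covers one parameter, one grade, no bleeding and no action taken. The PFS4 test, the MTD decision and the AESI stopping rule are unaffected.

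**What to change.** Add to Section 13.4.3:

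- Derive the worst post-baseline CTCAE v4.03 grade for platelets, ANC and hemoglobin directly from the collected laboratory values, regardless of adverse-event recording.
- Tabulate shifts from the last value before ruxolitinib to the worst grade on ruxolitinib, with a separate summary for the run-in. The baseline matters because subjects with marrow plasmacytosis of 50% or more may enter at 50,000/mm³, the edge of Grade 3.
- Keep the TEAE table alongside.

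The cost is some programming. No new samples are needed, because the Table of Events already schedules hematology on Days 1, 2, 8, 9, 15, 16 and 22 of each cycle. The toxicity rates may look less favourable.

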13.4.4 Exploratory Analyses

Logistic regression and Cox proportional hazards models will be used to assess the correlation between biomarkers and efficacy and toxicity outcomes. Exploratory objectives include exploring the correlation of toxicities and disease response with:

- Baseline serum cytokine profile
- Baseline PBMC JAK inhibition
- Baseline PBMC proteasome inhibition

Genomic studies will be performed on BM aspirate samples after sorting the CD138 positive and CD138 negative cells to understand mechanisms of carfilzomib sensitivity and resistance, along with modulation of the BM micro-environment. BM aspirate samples will be collected at:

- Baseline (screening)
- After Cycle #1 (between Days 20 – 27) of ruxolitinib
- At time of disease relapse and/or progression after initiation of ruxolitinib

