Study Objectives	The primary objective of Phase I is to establish the maximum tolerated dose (MTD) of ruxolitinib in combination with carfilzomib and dexamethasone. The primary objective of Phase II is to evaluate PFS at 4 months in multiple myeloma subjects who receive the combination treatment carfilzomib, dexamethasone and ruxolitinib. Secondary objectives include evaluation of objective response rate, clinical benefit rate, disease control rate, time to best response, PFS, overall survival, time to progression, duration of response (DOR), any occurrence of adverse events or serious adverse events while on study. Exploratory objectives include exploring the correlation of peripheral blood mononuclear cell (PBMC) SNPs and JAK inhibition with toxicities and treatment response, exploring the correlation of PBMC proteasome inhibition with toxicities and treatment response, and examining changes in biology of BM and BM plasma cells before and after treatment with global gene expression profiling/RNA seq/whole genome sequence/proteomics.
Sample	Up to 18 subjects in Phase I and an additional 30 subjects in Phase II
Inclusion/Exclusion	
(See protocol for complete inclusion/exclusion criteria)
 
Inclusion criteria:
 
 • Age \geq 18 years • Documented history of relapsed and or refractory multiple myeloma with $>$ 2 lines of therapy and evidence of relapse or progression within 60 days of a carfilzomib containing regimen at dose \geq 27 mg/m² • Measurable disease • Evidence of adequate bone marrow reserves • Evidence of adequate hepatic, renal, and cardiac function 
Exclusion Criteria:

	
 • Non-secretory multiple myeloma • Known amyloidosis • Known POEMS syndrome • Clinically significant illness that, in the opinion of the Investigator, places the subject at unacceptable risk for adverse outcome if he/she were to participate in the study • Pregnant or breastfeeding • Known human immunodeficiency virus (HIV) infection • Active hepatitis B and/or hepatitis C infection • “Currently active” second malignancy, other than non-melanoma skin cancer and carcinoma in situ of the cervix

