1.3 Exploratory Objectives

Exploratory objectives include the following:

- Explore the correlation of serum cytokine profile with toxicities and treatment response
- Explore the correlation of PBMC proteasome and JAK inhibition with toxicities and treatment response
- Examine changes in biology of BM and BM plasma cells before and after treatment by RNA sequencing

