- l) Blood and bone marrow samples will be collected for correlatives prior to study treatment initiation (collection is recommended after eligibility is established; baseline samples may be collected during screening or pre-treatment on C1D1); Cycle 1 of ruxolitinib, between Day 20-27; and at disease relapse or progression after ruxolitinib has been initiated. Blood only will be collected on C1D8 of ruxolitinib. These correlative labs include serum cytokines panel, peripheral blood mononuclear cells (PBMC) for proteasome inhibition, and PBMCs for JAK inhibition. Approximately 28 mLs of blood will be collected (please refer to the Correlative Guidelines for the type of tubes required) and will be sent to the LCI HOT lab. A minimum of 12 mL (first or second pull permitted) of bone marrow aspirate will be collected and sent to the LCI HOT lab. Note: ruxolitinib must have been initiated to collect correlative samples post-baseline (do not collect post-baseline correlative samples on subjects receiving study treatment in Phase II/Run-In period). Every effort should be made to collect post-baseline correlative samples prior to carfilzomib and dexamethasone administration; after the morning ruxolitinib dose and before the afternoon dose of ruxolitinib. Correlatives collected during screening do not need to be re-collected in the event that the screening period extends beyond 21 days.
- m) Known or suspected plasmacytomas are to be assessed at baseline, as clinically indicated and to confirm response and/or progression. FDG-PET is not required but suggested. The same method of evaluation should be used throughout the study (CT/MRI/PET). Phase II/Run-In subjects who cross over to Phase II/Ruxolitinib only: For subjects with plasmacytomas present at screening, imaging using the same modality utilized at screening will be repeated prior to initiating ruxolitinib (a new baseline will be established).
- n) Skeletal survey includes plain X-rays of (including skull, all long bones, pelvis and chest) required if previous survey >12 weeks from study entry and at any time when clinically indicated.
- o) See section 5 for complete details on study drug administration, dose modifications and start of a new cycle of therapy.
- p) Concomitant medications and procedures: - all procedures and medications within 14 days prior to first dose until 30 days after the last dose.

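### The exploratory models name only pre-treatment JAK and proteasome inhibition as covariates, so they do not address the drug-inhibition objective for which on-treatment samples are drawn

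*Combined protocol and SAP*

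**What the plan says.** Among its exploratory objectives, Section 1.3 has: "Explore the correlation of PBMC proteasome and JAK inhibition with toxicities and treatment response". The Study Objectives row of the protocol summary likewise includes "exploring the correlation of PBMC proteasome inhibition with toxicities and treatment response". Neither is limited to baseline.

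Section 13.4.4 opens with a general model statement: "Logistic regression and Cox proportional hazards models will be used to assess the correlation between biomarkers and efficacy and toxicity outcomes". The list that follows gives "Baseline PBMC JAK inhibition" and "Baseline PBMC proteasome inhibition". It names no on-treatment inhibition value and no change from baseline.

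Footnote l of the Table of Events (Section 18.5) defines the samples. Baseline comes before treatment: "baseline samples may be collected during screening or pre-treatment on C1D1". Later samples are taken in "Cycle 1 of ruxolitinib, between Day 20-27; and at disease relapse or progression after ruxolitinib has been initiated". In addition, "Blood only will be collected on C1D8 of ruxolitinib". The assays named for this blood include PBMC proteasome and JAK inhibition. Where possible, post-baseline draws are to fall between the two daily ruxolitinib doses and ahead of carfilzomib and dexamethasone. None are taken during the Run-In.

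**The concern.** The objective asks whether the degree of pathway inhibition relates to toxicity and response. The analysis section ties that question to a value measured before the subject has taken any study drug. Followed as listed, the logistic and Cox models would relate outcome to assay error, constitutive pathway activity or the residue of earlier treatment.

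The sampling schedule does look designed to capture drug effect. Because the analysis section does not name those samples, an analyst who used them would choose the time point, the metric and the handling of early events after seeing the data. Even for an exploratory aim, that weakens what can be said about a pharmacodynamic relationship.

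**Working it through.** The plan gives no sample size, power or error rate for this analysis, so there is no stated figure to reproduce. The check compares sections and adds some simple arithmetic.

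**1. Objective, covariate and sample**

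- Objective (Section 1.3): inhibition, no time point.
- Covariates (Section 13.4.4): baseline JAK inhibition and baseline proteasome inhibition.
- Baseline sample (Section 18.5, footnote l): screening, or C1D1 before treatment.
- On-treatment samples (same footnote): C1D8 and Day 20-27 of ruxolitinib, and at relapse or progression.

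**2. What a baseline covariate can carry**

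Inhibition by study ruxolitinib in a sample drawn before the first dose is zero for every subject. A constant covariate merges with the intercept in a logistic model and cancels from the Cox partial likelihood, so neither model yields a coefficient for drug effect. Any spread seen at baseline comes from another source: assay error, constitutive activity or earlier therapy.

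For the proteasome the same holds for study carfilzomib. Earlier carfilzomib is different. Section 3.1.1 requires prior carfilzomib, the eligibility criteria state no minimum washout from it, and Section 2.2.2 describes its binding as irreversible. Some residual inhibition is therefore possible, but it would be carry-over.

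**3. What the on-treatment samples measure** (nominal days, carfilzomib on Days 1, 2, 8, 9, 15 and 16)

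- C1D8, drawn before that day's carfilzomib: 8 − 2 = 6 days, about 144 hours, after the previous dose.
- Day 20-27: 20 − 16 = 4 to 27 − 16 = 11 days, about 96 to 264 hours, after the previous dose.
- Section 2.2.2 reports proteasome inhibition lasting at least 48 hours and gives no upper limit. These proteasome values are troughs.
- Section 2.4.2 puts peak inhibition of STAT3 phosphorylation at 2 hours after ruxolitinib, with return to near baseline by 10 hours. JAK values therefore depend on hours since the morning dose.

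**4. Run-In subjects**

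Their baseline correlative sample precedes study carfilzomib and predates ruxolitinib by at least one 28-day cycle, longer for responders who stay on the two-drug regimen until progression. Direct-entry subjects have no such gap. The disease baseline is reset before ruxolitinib (Sections 8.3.1 and 13.2); the correlative baseline is not.

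**5. Cost of a landmark at Day 28**

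Assume exponential PFS with the two medians in Section 13.1.2 and a month of 30.4 days, so that Day 28 is 28 / 30.4 = 0.92 months. The proportion with an event by then is 1 − 2^(−0.92 / median).

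- Median 2 months: 1 − 2^(−0.46) = about 27%.
- Median 4 months: 1 − 2^(−0.23) = about 15%.

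Disease is assessed by cycle, so detected events could be fewer or fall later than these figures suggest.

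**The case against.** The strongest defence is that the opening sentence of Section 13.4.4 covers biomarkers in general and the list is introduced as inclusive. The on-treatment samples are scheduled, their assays are named, and nothing bars their use. A reader might infer that the objective cannot be answered at all. The documents do not support that: the data will exist, and the gap is that no on-treatment covariate is named.

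A reader might also infer that baseline inhibition is zero in everyone by definition. That holds for ruxolitinib's effect, but not for proteasome inhibition in subjects previously given carfilzomib. The assay is not described either, so the wording may be a loose term for baseline pathway activity. If so, the term needs defining, and the listed covariate still does not measure drug effect.

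It is also fair to say that renaming the covariates does not settle the pharmacodynamic question. The on-treatment proteasome values are late troughs, and the documents do not show how much drug effect remains at those times. This stands, and it is why dose timing has to be recorded and the values labelled.

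Finally, a reader might count 18 + 30 = 48 subjects as contributing unused samples. Those are targets for evaluable subjects: enrolment can exceed them, and Run-In subjects who never start ruxolitinib give no post-baseline sample.

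**Conclusion.** The point holds in a limited form. Section 13.4.4 names covariates that cannot carry the study-drug effect that Section 1.3 asks about, and it omits the scheduled samples that could. This is decisive for JAK. For the proteasome, a baseline value could reflect carry-over from earlier therapy, which is still not the effect of study treatment. The conclusion assumes that inhibition means reduction caused by study drug; if the assay defines it otherwise, the plan should say so.

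Severity is low. The analysis is exploratory, and the primary endpoint, the two-stage rule, the sample size and the error rates do not depend on it.

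**What to change.** In Section 13.4.4:

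- Define inhibition for each assay, with baseline JAK and proteasome activity as the reference and as a separate covariate.
- Replace the two baseline inhibition covariates with change from that reference at C1D8 and at Day 20-27 of ruxolitinib.
- Record time since the last ruxolitinib and carfilzomib doses, account for it in the models, and label the proteasome values as troughs.
- In the Cox models, use a landmark or a time-dependent covariate, because these values arise after treatment start. Relate each value only to toxicities and responses after the sample.
- Note whether each subject came through the Run-In.

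No new samples are needed. The cost is SAP wording, recording of dose and draw times, and some analysis work. Subjects with events before sampling leave a landmark model (about 15% to 27% by Day 28 on the assumptions above). Toxicities early in Cycle 1, including any DLT before the sample, are not counted in these models. The choice between a landmark and a time-dependent covariate should be made before the data are examined.
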